**Table 2: Imputation Method for Each Endpoint and Analysis Type**

Endpoint	Analysis	Imputation/Censoring Method
Primary Endpoint		
Survival without mechanical ventilation in subjects who are < 85 years old, have baseline clinical status of 5 or 6, and baseline CRP < 150 mg/L.	Primary, additional sensitivity and subgroup	
 
Subjects who complete follow-up without mechanical ventilation or death or who have the event after Day 29 will be considered non-events.
 
Subjects who die or progress to mechanical ventilation after Day 29 will be considered non-events.
 
Subjects whose last assessment in the study is before Day 29 and before experiencing death or progression to mechanical ventilation will have missing event data for this endpoint and multiple imputation will be used to impute the missing data. See Section 6.5 for details.
 
Subjects whose last assessment in the study is before Day 29 but within window for Day 29 (i.e., Day 26, 27, 28) and before experiencing death or progression to mechanical ventilation will be considered non-events regardless of their discharge status.
 

	Sensitivity 1	
 
Subjects who complete follow-up without mechanical ventilation or death or who have the event after Day 29 will be considered non-events.
 
Subjects who die or progress to mechanical ventilation after Day 29 will be considered non-events.
 
Subjects whose last assessment in the study is before Day 29 and before experiencing death or progression to mechanical ventilation and were discharged to a location other than LTAC, hospice care, or other hospital will be considered non-events.
 
Subjects whose last assessment in the study is before Day 29 and before experiencing death or progression to mechanical ventilation and either had no post-baseline data or were still hospitalized or were discharged to LTAC, hospice care, or other hospital will have missing event data for this endpoint and multiple imputation will be used to impute the missing data. See Section 6.5 for details.
 
Subjects whose last assessment in the study is before Day 29 but within window for Day 29 (i.e., Day 26, 27, 28) and before experiencing death or progression to mechanical ventilation will be considered non-events regardless of their discharge status.
 

	Sensitivity 2	
 
Subjects who complete follow-up without mechanical ventilation or death or who have the event after Day 29 will be considered non-events.
 
Subjects who die or progress to mechanical ventilation after Day 29 will be considered non-events.
 
Subjects whose last assessment in the study is before Day 29 and before experiencing death or progression to mechanical ventilation will have missing event data for this endpoint and multiple imputation will be used to impute the missing data. See Section 6.5 for details.
 
Subjects whose last assessment in the study is before Day 29 but within window for Day 29 (i.e., Day 26, 27, 28) and before experiencing death or progression to mechanical ventilation will be considered missing and imputed using multiple imputation as described in Section 6.5.
 

Key Secondary Endpoints		
Time to mechanical ventilation or death up to and including Day 29 in subjects who are < 85 years old, have baseline clinical status of 5 or 6, and baseline CRP < 150	Primary and subgroup	
 
Use the complete data for ordinal score to define survival without mechanical ventilation.
 
All subjects whose last assessment in the study is before Day 29 and before progression to mechanical ventilation or death will be considered non-events and censored at the date of their last observed assessment.
 
Subjects who complete follow-up without mechanical ventilation or death will be censored at the expected study Day 29.
 

## Appendix 6 BET-B

Endpoint	Analysis	Imputation/Censoring Method
mg/L.	Sensitivity	
 
Use the complete data for ordinal score to define survival without respiratory failure.
 
Subjects whose last assessment in the study is before Day 29 and were discharged to a location other than LTAC, hospice care or other hospital, or progressed to mechanical ventilation or death after Day 29 will be considered non-events and censored at Day 29.
 
Subjects whose last assessment in the study is before Day 29 and before progression to mechanical ventilation or death and without being discharged to a location other than LTAC, hospice care or other hospital at their last assessment will be considered non-events and censored at the date of their last observed assessment.
 
Subjects who complete follow-up without mechanical ventilation or death will be censored at the expected study Day 29.
 

Time to Sustained Recovery up to Day 60 in subjects who are < 85 years old, have baseline clinical status of 5 or 6, and baseline CRP < 150 mg/L.	Primary and subgroup	
 
Use the complete data for ordinal score to derive sustained recovery.
 
Subjects whose last assessment in the study is prior to Day 60 prior to recovery will be considered not recovered and censored at the date of last follow-up.
 
Death prior to recovery will be considered not recovered and censored at expected study Day 60.
 

	Sensitivity	
 
Use the complete data for ordinal score to derive sustained recovery.
 
Subjects whose last assessment in the study is prior to Day 60 after discharge from the hospital to a location other than LTAC, hospice care or other hospital will be treated as recovered by Day 60. Their time to recovery will be the day the time of their first observed/imputed recovery score (i.e; 1, 2, 3) or the day of discharge, whichever comes first.
 
Subjects whose last assessment in the study is prior to Day 60 without being discharged from the hospital to a location other than LTAC, Hospice care or other hospital at their last assessment will be considered not recovered and censored at the date of last follow-up.
 
Death prior to recovery will be considered not recovered and censored at expected study Day 60.
 

Survival without mechanical ventilation for all subjects in ITT population	Primary, sensitivity, and subgroup	
 
Use the same imputation methods as those used for the primary endpoint of BET-B
 

Time to Sustained Recovery up to Day 60 for all subjects in ITT population	Primary, sensitivity, and subgroup	
 
Use the same imputation methods as those used for the analysis of time to recovery endpoint based on the primary subgroup of BET-B
 

Other Secondary Endpoints and Exploratory Endpoints		
The analysis described for the other secondary efficacy and safety endpoints along with exploratory endpoints in the Master SAP will be followed. Refer to Table 7 in the master SAP for addition details regarding imputation methods to be used for those endpoints.		

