## 6.5. Missing Data

For the primary endpoint of incidence of mechanical ventilation or death, subjects who are lost to follow-up before Day 29 prior to having an event and have their last assessment within window for Day 29 (i.e., Day 26, 27, 28) will be considered as non-events by Day 29 regardless of their discharge status at that time.

Remaining missing data for subjects lost to follow-up after discharge, while still hospitalized, or with no post baseline data will be imputed using multiple imputation. The main sensitivity analysis will consider subjects missing data while discharged as non-events and use a similar multiple imputation as the primary analysis for remaining missingness. Additional sensitivity analyses of the primary endpoint will use the same imputation approach as the primary analysis on different analysis populations and using different covariates in the final model.

Two secondary analyses of the primary endpoint will be conducted: the first is based on targeted maximum likelihood estimation (TMLE), and the second is a multiple imputation approach that uses TMLE for analysis of each imputed dataset. These approaches are described in Section 6.5.2.

Analysis of time to event endpoints (i.e., sustained recovery, time to improvement, time to mechanical ventilation or death) will be based on observed ordinal score along with discharge and death information. Refer to Table 2 for additional details regarding censoring and handling of missing data for all endpoints.

Some analyses of ordinal score such as ordinal scores over time described in Section 6.5.1 of the master SAP will be performed based on the complete dataset of ordinal score created using the following steps:

- All planned timepoints after death are assigned a score of 8
- Intermittent missingness:
  - Impute the intermittent missing ordinal score as 1 if the scores reported before and after the missing value are both 1 and no change in oxygen use or hospitalization status after discharge to a location other than hospice, long term acute care or other hospital.
  - Impute the intermittent missing ordinal score as 2 after discharge to a location other than hospice, long term acute care or other hospital if the subject doesn't fall into the category above and subject is not hospitalized at the time point.
  - Remaining intermittently missing data imputed using last observation carried forward.

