- All remaining missing ordinal scores after last assessment imputed using last observation carried forward.

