### **8.2.2. Time to Sustained Recovery Up to and Including Day 60 for Primary Endpoint Subgroup in the ITT Population**

Recovery will be defined as having a value of 1, 2, or 3 on the clinical status 8-point ordinal scale or discharge from the hospital to a location other than LTAC, hospice care, or other hospital. The time to sustained recovery will be defined as the elapsed time (in days) from Study Day 1 to the day prior to the earliest recorded day at which a subject reaches recovery and doesn't worsen (ordinal score  $> 3$ ) up to and including Study Day 60. This analysis will be conducted on the ITT population for those subjects who at baseline have a clinical status score of 5 or 6, CRP $<150$  mg/L, and age $\leq 85$  years. For the primary analysis of this endpoint, all subjects lost to follow-up or terminated early prior to recovery will be considered not recovered and censored at the date of their last observed assessment, regardless of their discharge status. As sensitivity analysis of this endpoint, any subjects that are lost to follow-up or terminated early prior to recovery and were discharged to a location other than LTAC, hospice care or other hospital will be considered recovered by study Day 60 with a time to recovery of time of discharge or time of first score of 1, 2, or 3, whichever comes first, while subjects that are lost to follow-up or terminated early before Day 60 before recovery, were still hospitalized or were discharged to LTAC, hospice care or other hospital at their last assessment will be considered not recovered and censored at the date of their last observed assessment.

Refer to [Table 1](#) for a list of covariates and subgroup analyses for this endpoint. Refer to [Table 2](#) for imputation methods to be applied to this endpoint.

The primary analysis time to sustained recovery up to and including Study Day 60 conducts a score test to compare treatment to control up to and including Study Day 60. The treatment median survival time, confidence intervals and p-value from the score test will be presented ([Table 10](#)). Restricted mean recovery time estimates will be provided for each treatment group and actual baseline ordinal score stratum as well as the difference in restricted mean recovery time between treatment groups within each of the baseline ordinal score strata ([Table 12](#)).

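### SAP Table 2's primary row for time to sustained recovery does not match SAP 6.5, 8.2.2 and Table 10 footnote a, and can be programmed to count subjects lost after a good discharge as recovered; Table 10 footnote b contradicts the sensitivity rule

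*SAP*

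**What the plan says.** Time to sustained recovery is key secondary 2 (primary subgroup) and key secondary 4 (all subjects), each tested at .049 in fixed order (SAP 6.8). SAP 3.2.2 requires a score of 1 to 3 with no return to 4 or higher through Day 60, so confirming it takes follow-up to Day 60. Below, a good discharge is one to a place other than LTAC, hospice or another hospital. Four places say how lost subjects are coded.

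- **SAP 6.5** says that analysis of time-to-event endpoints, sustained recovery among them, "will be based on observed ordinal score along with discharge and death information". It then directs the reader onward: "Refer to Table 2 for additional details regarding censoring and handling of missing data for all endpoints". A separate paragraph says that some ordinal-score analyses "will be performed based on the complete dataset of ordinal score created using the following steps". The last step reads: "All remaining missing ordinal scores after last assessment imputed using last observation carried forward".
- **SAP 8.2.2**, primary analysis: subjects lost "prior to recovery will be considered not recovered and censored at the date of their last observed assessment, regardless of their discharge status". Only its sensitivity analysis counts good discharges as recovered, dated at discharge or first score of 1 to 3, whichever is earlier. It too refers to Table 2.
- **SAP Table 2**, primary row: "Use the complete data for ordinal score to derive sustained recovery". The next bullet censors subjects lost *prior to recovery* at last follow-up and does not mention discharge status. The sensitivity row says: "Their time to recovery will be the day the time of their first observed/imputed recovery score", or the discharge day if earlier. For key secondary 4: "Use the same imputation methods as those used for the analysis of time to recovery endpoint based on the primary subgroup of BET-B".
- **SAP Table 10**: footnote a (initial model) censors subjects lost before recovery at last assessment. Footnote b (Sensitivity Analysis 1) calls good discharges recovered and censors them at Day 60.

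**The concern.** A programmer is sent to Table 2 from both 6.5 and 8.2.2, and finds there a data source that 6.5 does not give to this endpoint. The only definition of complete ordinal data in this SAP carries the last score forward, and Table 2's own sensitivity row mentions imputed scores. If a last score of 2 is carried to Day 60, the subject meets the definition of sustained recovery, is no longer lost before recovery, and escapes the censoring bullet. The discharge clause in 8.2.2 that would block this is missing from the row.

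At stake is whether two confirmatory tests are the ones that 8.2.2 describes. Under the literal reading the planned sensitivity analysis would also repeat the primary for most of the subjects it was meant to examine. Footnote b is a separate fault: in a time-to-recovery model, censoring at Day 60 is the coding that Table 2 gives to deaths.

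**Working it through.** **1. Plan's own figure.** The documents give no power, event count or loss rate for sustained recovery. The only stated power is for the primary endpoint, and it reproduces. At a control rate of 16%, odds = 0.16/0.84 = 0.1905; divided by 2.5 = 0.0762; treated rate = 0.0762/1.0762 = 7.08%. With 200 per arm and two-sided .049, a pooled two-proportion test has 79.7% power (stated 80%). At 21% against 9.61% it has 88.7% (stated 89%). The point does not depend on this.

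**2. The rules applied to example subjects.** Each has score 5 through Day 5 and goes home on Day 6. Time follows 8.2.2, which counts to the day before the first recovery day.

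| Subject | 8.2.2 / 6.5 primary | Table 2 primary, literal | Sensitivity rule (8.2.2, Table 2) | Footnote b |
|---|---|---|---|---|
| Score 2 from Day 6, last contact Day 15 | censored Day 15 | event Day 5 | event | censored Day 60 |
| Score 2 from Day 6, last contact Day 29 with score 1 | censored Day 29 | event Day 5 | event | censored Day 60 |
| No contact after discharge, last recorded score an in-hospital 5 | censored Day 6 | censored Day 6 | event at discharge | censored Day 60 |
| Followed to Day 60, score 1 | event Day 5 | event Day 5 | event | event |

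The first two rows are the mismatch. The third shows its limit: a carried-forward 5 creates no recovery, so the primary and sensitivity analyses still differ for that subject.

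**3. Size for key secondary 2.** 4,000 trials were simulated per scenario.

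- Inputs from the documents: 200 per arm; ventilation or death in 16% against 7% (Protocol 9.1); 75% of controls recovered by Day 8 (from the LIVE-AIR discharge figure, Protocol 1.1.1); 65% of those with the event die (13.8/21.2, Protocol 1.1).
- Assumed: equal post-discharge loss of 1%, 2% or 5%; last contact at Day 8, 15, 22 or 29, or later if recovery was later; ventilated survivors recover at least 10 days after the event; covariate effects.
- Test: Cox score test, Efron ties, the four SAP Table 1 covariates, two-sided .049. Only trials in which the primary and key secondary 1 both passed are counted (78 to 80% of trials).

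About 4, 7 and 18 of 400 subjects are coded differently at 1%, 2% and 5% loss.

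| Added effect on recovery speed (rate ratio) | Power, event vs censored: 1% loss | 2% loss | 5% loss | Decision differs (1/2/5% loss) |
|---|---|---|---|---|
| 1.0 | 69 vs 66% | 69 vs 63% | 70 vs 56% | 9/14/22% |
| 1.15 | 92 vs 90% | 92 vs 86% | 93 vs 79% | 5/8/16% |
| 1.3 | 99 vs 98% | 99 vs 97% | 99 vs 92% | 1/2/8% |

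Power is high even at a rate ratio of 1.0 because fewer treated subjects are ventilated or die, so more recover. With no effect of any kind and no hierarchy applied, the codings reject equally often: 5.4/6.2/6.0% (event) and 5.3/6.1/6.1% (censored).

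Range checks at rate ratio 1.0, for 2% and 5% loss:

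- 60% recovered by Day 8: 67 vs 63% and 68 vs 57%.
- 76% of events fatal (6.5/8.5): 72 vs 66% and 71 vs 57%.
- Control rate 21%: 80 vs 76% and 79 vs 66%.

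Monte Carlo error is at most about 1 point.

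**4. Unequal loss.** A smaller, unadjusted run (150 trials per scenario, input rate ratio 1.3) gave mean hazard ratios, censored against event, of 1.05 vs 1.17 with loss of 5% on placebo and 10% on active, and 1.24 vs 1.16 with these reversed. Lost subjects in that run had truly recovered, so the event coding is right by construction. It shows that the choice matters more when loss differs by arm, not which coding is correct.

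**5. Footnote b.** At 5% loss and rate ratio 1.0 the geometric mean hazard ratio is 1.22 in the censored primary and 1.25 under the sensitivity rule of 8.2.2, but 1.21 under footnote b, which moves the other way. Significance under footnote b differs from the correct sensitivity result in 16% of trials reaching the test at 2% loss and 27% at 5% (rate ratio 1.3: 3% and 11%).

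**The case against.** The strongest reply is that the contrast reads one text literally and the other by its purpose. SAP 8.2.2 defines recovery as a score of 1 to 3 or a good discharge. Taken literally, a subject sent home on Day 6 has already recovered, and 8.2.2 would yield an event as well. That reading would leave 8.2.2's sensitivity group empty and its discharge clause without work to do, so *prior to recovery* must there mean before sustained recovery is confirmed. Table 2's censoring bullet uses the same phrase. Given the same meaning, it censors too. This stands: the row can be read either way.

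Other points also carry weight. The Table 2 row for time to ventilation or death opens with the same reference to complete data and then censors at last observed assessment, so the phrase need not override censoring. In that row it is harmless, because a carried-forward score below 7 cannot become a 7 or 8. SAP 6.5, 8.2.2 and Table 10 footnote a all point to censoring, which makes misprogramming less likely. SAP 6.5 ties the complete dataset to analyses in the master SAP, which was not available. Protocol 9.1 and SAP 5 expect little missing data.

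None of this removes the mismatch. Table 2 still names a data source that differs from 6.5 and omits the discharge clause, and its sensitivity row brings in imputed scores. Footnote b cannot be rescued in this way, since both Table 2 and 8.2.2 contradict it.

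**Conclusion.** Two corrections are needed before unblinding. Table 2's primary row should be brought into line with 6.5, 8.2.2 and footnote a; it affects key secondary 2 and, by inheritance, key secondary 4. Footnote b is wrong as written: a Cox model would treat good discharges lost to follow-up as never recovered.

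For key secondary 2 the power difference is about 1 to 6 points at an assumed 1 to 2% equal loss and 7 to 14 points at 5%. For equal loss at those rates these are upper figures, because every lost subject was assumed to have a last score of 1 to 3 and so to switch. The loss rates are assumptions.

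A reader might infer more than the documents support:

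- That Table 2 definitely makes these subjects events. Its censoring bullet allows the opposite reading.
- That the sensitivity analysis becomes empty. It loses most of its contrast with the primary, not all, because subjects with a last recorded score of 4 or higher stay censored in the primary.
- That type I error is inflated. With equal loss the two codings reject equally often under no effect.
- That the primary endpoint is touched. It is not, and these tests are reached only if the earlier ones succeed.

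**What to change.** In Table 2's primary row for sustained recovery, replace the reference to complete data with observed ordinal score plus discharge and death information, and state that censoring at last assessment applies whatever the discharge status. In both Table 2 and 8.2.2, define *prior to recovery* as before sustained recovery is confirmed through Day 60. Key secondary 4 then follows through its existing cross-reference. If the sponsor prefers event coding as primary, change 6.5, 8.2.2 and Table 10 footnote a to match, and keep the censored coding as the sensitivity analysis.

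Reword Table 10 footnote b so that good discharges lost to follow-up are events at discharge or first score of 1 to 3, whichever comes first.

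Two minor edits: SAP 8.2.2 admits age up to and including 85 where the rest of the plan has under 85, and SAP 8.2.4 points to 8.2.1 (ventilation or death) where 8.2.2 is meant.

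The cost is SAP and footnote wording only. No data collection or design feature changes.

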3. OBJECTIVES AND ENDPOINTS

Table 4. BET-B Study Objectives

OBJECTIVES	ENDPOINTS (OUTCOME MEASURES)
Primary	
To evaluate the clinical efficacy of lenzilumab as assessed by survival without mechanical ventilation through Day 29 in subjects with ordinal scores 5 or 6 at baseline with a CRP<150 mg/L and age<85 years.	Occurrence of mechanical ventilation or death at any point through Day 29 in subjects with ordinal scores 5 or 6 at baseline with a CRP<150 mg/L at baseline and age<85 years, where the event is one of these two categories: 7. Hospitalized, on invasive mechanical ventilation or extracorporeal membrane oxygenation (ECMO);

OBJECTIVES	ENDPOINTS (OUTCOME MEASURES)
	8. Death.
Key Secondary (in order of testing)*	

To evaluate the clinical efficacy of lenzilumab as assessed by:
 
 1. Survival without mechanical ventilation through Day 29 in subjects with ordinal scores 5 or 6 at baseline with a CRP<150 mg/L and age<85 years. 	
Time to ventilation or death Day 29 in subjects with ordinal scores 5 or 6 at baseline with a CRP<150 mg/L at baseline and age<85 years, where the event is one of these two categories:
 
 7. Hospitalized, on invasive mechanical ventilation or extracorporeal membrane oxygenation (ECMO); 8. Death.

 2. Time to sustained recovery compared to the control arm in subjects with ordinal scores 5 or 6 at baseline with a CRP<150 mg/L and age<85 years. 	
Day of recovery is defined as the first day on which the subject satisfies 1 of the following 3 categories from the ordinal scale (and does not return to a score of 4 or higher for the remainder of the study period):
 
 1. Not hospitalized, no new or increased** limitations on activities; 2. Not hospitalized, but new or increased limitation on activities and/or requiring new or increased home oxygen, CPAP, or BiPAP; 3. Hospitalized, not requiring new or increased supplemental oxygen - no longer requires ongoing medical care.

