### 3.2.2. Secondary Endpoints

1. Time to mechanical ventilation or death up to and including Study Day 29 for subjects < 85 years old with baseline ordinal score of 5 or 6 and baseline CRP < 150mg/L. That is time to a clinical status of:
  - Hospitalized, on invasive mechanical ventilation or ECMO (ordinal score 7); or
  - Death (ordinal score 8).
2. Time to sustained recovery as defined as the first day on which the subject who is < 85 years old with baseline ordinal score of 5 or 6 and baseline CRP < 150 mg/L satisfies 1 of the following 3 categories from the clinical status ordinal scale (and does not return to a score of  $\geq 4$  up to and including Study Day 60):
  - Not hospitalized, no new or increased limitations on activities (ordinal score 1);
  - Not hospitalized, but new or increased limitation on activities and/or requiring new or increased home oxygen, CPAP, or BiPAP (ordinal score 2);
  - Hospitalized, not requiring new or increased supplemental oxygen - no longer requires ongoing medical care (ordinal score 3).
3. Proportion of subjects at Day 29 that did not satisfy the following criteria up to and including Study Day 29:
  - For subject with baseline clinical status of 5 or 6:
    - Hospitalized, on invasive mechanical ventilation or ECMO (ordinal score 7);
    - Death (ordinal score 8); or
  - For subjects with baseline clinical status of 7:
    - Death (ordinal score 8).
4. Time to sustained recovery will be analyzed including all subjects randomized to BET-B including any shared controls from other stages.

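### The sensitivity rule for sustained recovery omits the no-worsening condition for subjects lost after a good discharge, so an observed relapse before the final discharge is passed over when recovery is dated

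*SAP*

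**What the plan says.** **The endpoint.** Protocol Section 3, Table 4, takes the first day at a score of 1, 2 or 3, provided the subject stays there: "and does not return to a score of 4 or higher for the remainder of the study period". SAP 3.2.2 opens its definition with "Time to sustained recovery as defined as the first day on which the subject" and applies the same condition through Day 60. SAP 8.2.2 adds a good discharge as a form of recovery and keeps the no-worsening condition.

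**The sensitivity analysis.** The Sensitivity row of SAP Table 2 has three relevant parts:

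- It begins with a general instruction: "Use the complete data for ordinal score to derive sustained recovery".
- A special rule follows for one group: "Subjects whose last assessment in the study is prior to Day 60 after discharge from the hospital to a location other than LTAC", hospice or another hospital. These subjects count as recovered by Day 60, dated at "the time of their first observed/imputed recovery score (i.e; 1, 2, 3) or the day of discharge, whichever comes first".
- Subjects not in good-discharge status "at their last assessment will be considered not recovered and censored at the date of last follow-up".

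SAP 8.2.2 states the special rule for "any subjects that are lost to follow-up or terminated early prior to recovery and were discharged to a location other than LTAC", hospice or another hospital, "with a time to recovery of time of discharge or time of first score of 1, 2, or 3, whichever comes first". Table 2 applies the same handling to key secondary 4, the all-subjects version.

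**The table shell.** Footnote b of the Table 10 shell describes the same sensitivity analysis differently. It has good discharges counted as recovered yet censored at Day 60.

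**The concern.** The sensitivity analysis should change one thing: how loss after a good discharge is handled. The primary analysis censors those subjects, and the sensitivity analysis credits them with recovery. Any difference between the two results could then be put down to the missing-data assumption.

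The special rule takes the earlier of two dates and attaches no condition about what happened afterwards. For a covered subject whose relapse is in the data, it moves from sustained recovery to first recovery. The sensitivity analysis then differs from the primary analysis in two respects for that subject, and an observed relapse has no bearing on the recovery date. Subjects with the same course who stay in the study until Day 60 are still dated by the sustained definition, so two definitions operate within one analysis.

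**Working it through.** The documents give no power, event count or other figure for sustained recovery, so there is nothing of the plan's own to reproduce. The check applies two rules to constructed score histories.

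- Literal rule = min(first day at score 1-3, day of discharge).
- Sustained rule = first day at score 1-3 or good discharge after which no score of 4 or higher is observed.

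| Constructed history | Literal rule | Sustained rule | Difference |
|---|---|---|---|
| A. No relapse; discharged Day 6; lost after Day 22 | Day 6 | Day 6 | 0 |
| B. Score 3 on Day 4; score 5 on Day 6; discharged Day 12; lost after Day 22 | Day 4 | Day 12 | 12 − 4 = 8 days early |
| C. Discharged Day 6; readmitted at score 5 on Day 10; discharged Day 15; lost after Day 29 | Day 6 | Day 15 | 15 − 6 = 9 days early |
| D. Discharged Day 6; readmitted at score 5 on Day 20; lost while in hospital | Day 6 if the special rule applied | Not recovered | Next bullet censors the subject, as the sustained definition requires |

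The rules part only when four things coincide: the subject reached 1-3 or was discharged, was then observed at 4 or higher, had a good discharge, and was lost before Day 60. In B and C the subject is again in a recovery state at last contact, so the error lies in the date.

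D shows an ambiguity. The special rule speaks of a last assessment after discharge. The censoring bullet speaks of discharge status at the last assessment. A subject discharged, readmitted and then lost could be placed under either.

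**How many subjects.** The planned subgroup is 400 (SAP Section 5). Loss and relapse rates are not stated, so both are assumed. Let L be the share lost after a good discharge, and R the share of those with an observed earlier relapse. Affected = 400 × L × R.

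- L = 2%, R = 2%: 400 × 0.02 × 0.02 = 0.16, about 0.2
- L = 5%, R = 5%: 400 × 0.05 × 0.05 = 1
- L = 10%, R = 10%: 400 × 0.10 × 0.10 = 4

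A simulation with heavier assumptions (5-10% relapse, 10-20% lost, relapse at 0.7 times the average rate on lenzilumab and 1.3 times on placebo) had 2, 4 and 7 affected subjects. The recovery hazard ratio, sustained dating versus literal rule, was 1.272 versus 1.267, 1.303 versus 1.295, and 1.328 versus 1.316. The shifts are 0.005, 0.008 and 0.012. Their direction follows from the assumed difference between arms in relapse.

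**Table 10 footnote b.** History A is an event at Day 6 under Table 2 and 8.2.2, but a censored observation at Day 60 under the footnote. That conflict concerns every subject lost after a good discharge, relapse or not: 400 × 0.02 = 8 to 400 × 0.10 = 40 subjects under the same assumed loss rates.

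**The case against.** Four points can be made for the plan.

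1. **The row already says to derive sustained recovery.** No sentence says that an observed relapse is to be ignored, and the opening bullet favours the sustained reading. This stands as evidence of intent. The same bullet also opens the primary row, however, and what follows is a specific dating instruction for this group. A programmer would reasonably code it as a minimum, so the row holds two instructions that disagree for subjects such as B and C.

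2. **SAP 8.2.2 limits the rule to subjects lost before recovery.** Subject B recovered on Day 12 and might fall outside it. This does not rescue the rule. In the same section the primary analysis censors subjects lost before recovery whatever their discharge status. That makes sense only if a good discharge followed by loss counts as loss before sustained recovery was confirmed. Table 2 does not carry the limit at all.

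3. **The subjects have recovered under either reading.** This largely stands. A reader might infer that the analysis credits recoveries that were not sustained. In B and C only the date is wrong, and in D the censoring bullet can withhold credit. The D-type ambiguity is the only route to a false recovery.

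4. **The effect is negligible and its direction unknown.** This stands. A reader might infer a bias in a known direction, but that needs an arm difference in relapse that the documents do not supply.

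**Conclusion.** The point holds as a wording defect of minor consequence. For subjects lost before Day 60 after a good discharge, Table 2 and SAP 8.2.2 leave out the no-worsening condition. Read literally, they date a subject with an observed relapse before that relapse, against the endpoint definition and against the row's own first bullet.

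A reader might conclude that the whole sensitivity analysis replaces sustained recovery with first recovery. The documents do not support that: the rule covers one loss pattern, and subjects followed to Day 60 keep the sustained definition.

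The effect is confined to the sensitivity analysis of key secondaries 2 and 4 and probably to a handful of subjects. That size rests entirely on assumed rates. SAP Section 5 expects little missing data, although it says so for the primary-endpoint sample size. The primary analysis of this endpoint does not use the rule, and the hierarchical test at .049 is unaffected. The disagreement with Table 10 footnote b is firmer, because it does not depend on relapse.

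**What to change.** Three edits to the SAP:

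1. In the Sensitivity row of Table 2 and in 8.2.2, date recovery for these subjects at the first score of 1-3 or good discharge after which no score of 4 or higher is observed through the last assessment. Describe the covered group identically in both places.
2. State that a subject who has been readmitted and is in hospital at the last assessment falls under the censoring bullet.
3. Reconcile Table 10 footnote b with Table 2 and 8.2.2, so that these subjects are events at their recovery date in all three places.

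The reference in Table 2 then carries the change to key secondary 4. The cost is a few sentences and one footnote, plus a matching line in the derivation program. No new data are needed, and no alpha or sample size changes.
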